Twelve drugs have been marketed for use as monotherapy in Italy. The first standard maintenance dosages of these drugs reported in the Italian National Formulary (www.codifa.it) are the following: carbamazepine, 800-1600mg; phenobarbital, 100mg; phenytoin, 300mg; valproate, 1000mg; lamotrigine, 200mg; levetiracetam 1000mg; oxcarbazepine, 600mg; topiramate, 100-200mg; gabapentin, 900-3600mg; ethosuximide, 1000-1500mg; zonisamide, 300mg; lacosamide 200mg.

Published reports and common experience show that exposing patients to long-term treatment with higher dosages of antiepileptic drugs (AEDs) increases the risk of adverse effects and has a negative impact on quality of life (Gilliam, 2002). When AED treatment is given at low doses, adverse effects are no different from untreated individuals (Perucca et al, 2011). There are no published studies comparing low to standard doses of AEDs.

In 1996 the promoter started a nationwide randomized pragmatic trial comparing low to standard doses of carbamazepine, phenobarbital, phenytoin and valproate in children and adults with newly diagnosed epilepsy. Drug selection was left to the caring physician's judgment. 122 patients were randomized by 17 centers and followed for up to 36 months. 80 cases had complete and evaluable data. 73% of cases receiving low daily doses and 79% of those receiving standard doses entered 24-month remission. Compared to low doses, patients on standard doses had a higher chance of treatment change, mostly due to adverse events. In the last two years, the PI investigated the therapeutic habits of 26 Italian epilepsy centers in terms of initial maintenance dose for each of the AEDs used as monotherapy in newly diagnosed patients. 19 of them replied, 12 opting for low doses and 7 for standard doses. The maintenance dose of each drug varied significantly as follows: carbamazepine, 400-1200; phenobarbital, 50-150; phenytoin, 150-400; valproate, 500-1500; lamotrigine, 50-400; levetiracetam 500-2000; oxcarbazepine, 450-1800; topiramate, 100-400; gabapentin, 600-3200; zonisamide, 100-400; lacosamide 100-200 mg.

On this background, our research hypothesis is that low doses of AEDs in adults with newly diagnosed previously untreated focal and focal-to-bilateral epilepsy are at least as effective as

standard doses but carry a significantly lower risk of adverse effects, are associated with a better quality of life and satisfaction, and translate into significant savings for the National Health System. The study can help define the lowest effective therapeutic strategy and, if possible, the lowest effective dose for each AED.

2. Study objectives

2.1. Primary objective

To demonstrate that the proportion of patients receiving a low dose of an AED and remaining seizure-free is not inferior to the proportion of patients who remain seizure-free after receiving a standard dose of the same drug.

2.2 Secondary objectives

To demonstrate that the proportion of patients experiencing intolerable drug-related adverse events is lower with a low than a standard dose.

To demonstrate that health-related quality of life (HRQOL) and satisfaction with treatment score higher with a low than a standard dose.

To demonstrate that, on a societal perspective, the treatment of newly diagnosed epilepsy with low AED doses will translate into savings in terms of contacts with the National Health System (in- and outpatient visits, drug expenditures).

2.3 Primary endpoint

The primary end-point is a treatment failure motivated by the need to change the assigned dose or the assigned drug for seizure relapse.

2.4 Secondary endpoints

Secondary endpoints include: 1. Treatment failure motivated by intolerable drug-related adverse events; 2. HRQOL total score at 12 months; 3. Patient's satisfaction at 12 months; 4. Total cost of health care resources consumed for the management of epilepsy during the first 12 months of the study.

3. Study design

This is a multicenter randomized pragmatic parallel-group single-blind non-inferiority trial. Italian epilepsy centers will participate in the study. Each center has been selected on the basis of high

standards in the management of epilepsy and on previous participation to studies coordinated by the PI.

3.1 Participating centers

The Promoter of the study is the Istituto di Ricerche Farmacologiche Mario Negri IRCCS.

The coordinating center for patients' enrolment is the ASST Monza Ospedale San Gerardo.

Satellite centers placed in the entire national territory will be involved in the study.

3.2 Inclusion criteria

Patients eligible for inclusion must satisfy all the following criteria:

1. Age 18 years or older;
2. Newly diagnosed previously untreated epilepsy, defined according to the ILAE definition (Fisher et al, 2014);
3. Having experienced focal and focal-to-bilateral seizures, defined according to the ILAE criteria (Commission, 1981);
4. Able to understand and comply with the study requirements and release a written informed consent.

3.3 Exclusion criteria

A patient will be excluded if at least one of the following criteria will be met:

1. Age less than 18 years;
2. Having experienced primarily generalized tonic and/or clonic seizures, or other (non-focal/focal-to-bilateral) seizure types;
3. Previous exposure to AEDs for a period > 7 days before randomization and a dose higher than the low dose of the study protocol
4. Requiring low or standard doses on account of individual needs;
5. Inability to understand the aims or modalities of the study;
6. Current pregnancy or planning to become pregnant during the study period (e.g. who are not post-menopausal, surgically sterile, or using inadequate birth control). A postmenopausal state is defined as no menses for 12 months without an alternative medical cause;
7. Previous treatment with an antiepileptic drug;
8. Women unable to practice contraception for the duration of the treatment.
9. Poor compliance with assigned treatments;
10. Refusal to release written informed consent;

11. The study investigators will receive the summary of product characteristics (SPC) available for each study drug. Patients cannot be enrolled in the study if the contraindications/warnings described in the SPC are met.

3.4 Randomization

After informed consent, eligible patients will be randomized to receive a low or a standard dose of the assigned drug. Randomization will be centralized at the Istituto Mario Negri IRCCS, Milano. Randomization sequence will be created using SAS 9.4 (SAS Institute, Cary, NC, USA) statistical software and will be stratified by center with a 1:1 allocation using random block sizes of 4. Each center will receive randomization scratch-cards.

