6.3 Patient numbering and treatment assignment

Eligible subjects will be enrolled and randomized during the same visit (Visit 1). At the end of this visit, if a subject fails to be randomized for any reason, the reason for not being randomized will be entered on the Screening Log.

Patients will be identified by a unique subject number, which will be assigned by the site investigator consecutively. The subject number will determine the allocation of treatment. The treatment will be assigned through a central randomization. The assigned treatment will be recorded in the source documents as well as in the subject's e-CRF. Once assigned, a subject number will not be reused for another patient. For all participants, the subject number will not be changed during the entire study.

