6.4 Treatment blinding

The study is single-blind. Only the evaluating physician will be blinded to the assigned treatment schedule.

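### Section 3.4 calls the block size random but names only 4; followed as written, unblinded sites could know roughly a quarter to a third of allocations in advance

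*Combined protocol and SAP*

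**What the plan says.** Section 3.4 states that "Randomization will be centralized at the Istituto Mario Negri IRCCS, Milano", that the sequence is "stratified by center with a 1:1 allocation using random block sizes of 4", and that "Each center will receive randomization scratch-cards". No second block size is given anywhere, and nothing says that the size is withheld from sites.

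Section 6.4 states that "Only the evaluating physician will be blinded to the assigned treatment schedule". Treating physicians and patients therefore know the arm.

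Section 6.3 states that "Patients will be identified by a unique subject number, which will be assigned by the site investigator consecutively" and that "The subject number will determine the allocation of treatment".

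Section 3.3, exclusion criterion 4, rules out a patient described as "Requiring low or standard doses on account of individual needs". Section 6 leaves the choice of drug to the caring physician.

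**The concern.** The 3.4 sentence contradicts itself, and the only reading that uses a size the protocol supplies is a fixed block of 4. With blocks running within center, the size in print, earlier allocations visible and numbers issued in order, a site can work out where each block ends.

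If the next arm is known or well guessed, the decision to enroll a particular patient now, later or not at all may depend on it. Two routes are open: the timing of enrolment, and exclusion criterion 4, which is discretionary and refers directly to dose. Either could make the arms differ at baseline in ways that later adjustment may not capture. In a non-inferiority trial, such a difference could push the comparison toward or away from the margin.

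**Working it through.** The documents give no figure for predictability, so there is none to reproduce.

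**Inputs.** Block size 4, 1:1, within center (3.4), so 2 low (L) and 2 standard (S) per block. Total 374 patients (10.6). The number of centers and the patients per center are not stated, so center size is varied below.

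**Certain allocations, complete block of 4.** There are 6 equally likely orderings. Two (LLSS, SSLL) fix the last two places; the other four fix only the last.
- Expected number certain = (2×2 + 4×1)/6 = 1.333 of 4 = 33.3%.
- By position: 0, 0, 1/3, 1.
- If every block were complete: 374/3 ≈ 125 allocations.

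**Best guess, complete block of 4.** The observer guesses the arm with more places left. Success by position is 1/2, 2/3, 2/3, 1, so (0.500 + 0.667 + 0.667 + 1)/4 = 2.833/4 = 70.8%, against 50% by chance.

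**Part-filled last blocks.** These lower both figures:

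| Patients at center | Certain | Best guess |
|---|---|---|
| 6 | 1.333/6 = 22.2% | (2.833 + 1.167)/6 = 66.7% |
| 10 | 2.667/10 = 26.7% | (5.667 + 1.167)/10 = 68.3% |
| 15 | 4.333/15 = 28.9% | (8.500 + 1.833)/15 = 68.9% |
| Any multiple of 4 | 33.3% | 70.8% |

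For centers with at least 4 patients, 22.2% is the lowest certain share. With 3 patients it is 0.333/3 = 11.1%; with 1 or 2 it is zero.

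**Varying sizes.** The sets are assumptions, since the protocol names none. Simulation used equally likely sizes and an observer who knows the set of sizes but not their order. Certain shares at 12 to 20 patients per center:
- 2 and 4: about 10%
- 4 and 6: about 6%
- 2, 4 and 6: about 3.5%
- 4, 6 and 8: about 2.4%

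For 4, 6 and 8, best-guess success compares with the fixed block of 4 at the same center size as follows:

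| Patients at center | Fixed 4 | Sizes 4, 6, 8 |
|---|---|---|
| 6 | 66.7% | 64.7% |
| 10 | 68.3% | 65.8% |
| 12 | 70.8% | 66.5% |
| 20 | 70.8% | 67.1% |

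Varying the sizes removes nearly all certainty but only 2 to 4 points of guessing success.

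**The case against.** **The word random may mean that varying sizes were intended.** This stands as a limit. If so, the certain share would be about 2% to 10%, depending on the sizes. The text still needs correcting, because anyone following it literally would program a fixed block.

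**One third is near the top of the range.** This also stands. It needs complete blocks and one person who follows every allocation at the center, so the range is the fairer statement.

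**Safeguards exist.** Section 3.6 puts eligibility, consent and baseline data before randomization. Section 6.3 sends the reason for non-randomization to the Screening Log. The sequence is produced centrally, and 10.4 plans Cox adjustment for baseline imbalance. These help, and withholding a patient at Visit 1 would leave a record. They do not reach a patient who is deferred or never approached, and adjustment covers only measured variables.

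**A reader might infer that higher-risk patients would be kept off low dose, favoring non-inferiority.** The documents do not support a direction. Section 1 reports that 12 of 19 responding Italian centers opted for low doses and 7 for standard, so preferences run both ways. Exclusion criterion 4 also removes a patient from the trial; it does not move that patient to the other arm.

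**A reader might also put a size on the bias.** Suppose 20% of patients are steered by best guess and high-risk patients relapse 30 points more often. If half of those steered are high-risk and half low-risk, in opposite directions, the relapse difference shifts by 0.20 × (2×0.708 − 1) × 0.30 = 2.5 points. If all are high-risk, the shift is 0.20 × 0.417/0.5 × 0.30 = 5.0 points. With no steering it is zero, and opposite preferences reverse the sign. Both inputs are assumptions absent from the documents, so the range runs from −5.0 to +5.0 points and supports no estimate.

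**Conclusion.** The point holds as a contradiction in 3.4 that, followed literally, makes allocation partly predictable: about 22% to 33% certain and 67% to 71% guessable at centers with at least 4 patients. It rests on three assumptions: 3.4 is carried out as worded, someone at the center tracks its allocations, and cards are used in number order. Predictability is an opportunity for selection bias and not evidence that it has occurred; its direction and size cannot be set from the documents. The sample size of 168 per arm and 374 in total is not affected. The point merits a change because the remedy costs little.

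**What to change.** In 3.4:

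- State that block sizes vary at random within center, without naming them. Keep the sizes only in a restricted file at the central randomization unit, and remove the figure 4 from the protocol sent to sites. Sizes 4, 6 and 8 are one example.
- State that the arm is revealed only after eligibility, consent and choice of drug are recorded, and that scratch-cards are used in strict order. Section 3.6 already covers the first two; the chosen drug is not in the 3.5 baseline list, and no rule governs card order. This step matters because varying sizes alone leaves best-guess success at about 65% to 67%.

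If enrolment has begun, apply the change to cards not yet issued and report it.

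**Cost.** A revised SAS list, replacement cards and a short amendment. With blocks of up to 8, the possible within-center imbalance rises from 2 patients to 4. This is a cheap improvement.

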3.5 Data collection at baseline and during follow-up

The following variables will be collected at admission by the evaluating physician: date of birth, sex, height, weight, arterial blood pressure, heart rate, family history of epilepsy, history of febrile seizures, date of onset of seizures, seizure type(s), epilepsy syndrome or non-syndromic epilepsy, neurological and psychiatric examination (coded as normal or abnormal), first interictal EEG (coded as normal, slow or epileptiform), imaging findings (coded as normal or abnormal for seizure etiology), relevant comorbidities, concurrent treatments, HRQOL (using the Italian version of the QOLIE-31 inventory; Beghi et al, 2005), patient satisfaction (PSQ-18), laboratory examinations if available (CBC, alanine aminotransferase, aspartate aminotransferase, gamma glutamyltranspeptidase, creatinine, alkaline phosphatase, calcium, phosphorus, sodium, potassium, ammonia, amylase). Each patient will be followed for 12 months. In the follow-up visits the same laboratory tests will be performed as per clinical practice or caring physician discretion, including the AED plasma concentration assay. Ad-hoc diaries will be given to each patient and/or caregiver for the collection of follow-up data. The diaries will include the number of seizures (with dates) and the type and severity of adverse events (with dates, outcome and actions). To preserve blindness, daily intake and timing of the assigned, but not the daily dose, will be recorded in the diaries. Any contact with the National Health System for the management of seizures and AEDs will be also noted in the diaries with dates. The contents of the diaries will be verified during each telephone contact by the evaluating physician and by the treating physician at the time of the face-to-face visits.

3.6 Baseline and follow-up visits

At the baseline visit (Visit 1), each patient with newly diagnosed epilepsy will be screened for eligibility. Patients satisfying all the selection criteria will be informed of the study aims and asked to release a written informed consent. All the baseline data will be collected in an electronic case report form (e-CRF) and the patient will be then randomized. Follow-up visits will be scheduled at the discretion of the caring physician but telephone contacts will be programmed at 4 weeks, 3, 6, 9 and a clinic on-site visit at 12 months. An interval of \pm 1 week for the visit schedule is permitted. During each contact/visit the patient will be asked to report any seizure recurrence, adverse event and any additional information deemed important for the management of the disease. Patients will be invited to read the diaries and verify if any missing or incomplete information was present.

4. Study duration

Study duration: 36 months as indicated below:

- Administrative and ethical procedures: 6 months.
- Duration of patient enrolment: 12 months.
- Follow-up period: 12 months from the date of randomization.
- Database lock and statistical analysis: 30th-35th month.
- Final report and data publication: 36th month.
- Planned start of enrolment: as soon as the Ethics committee approval and signed contract are in house.

The end of study is considered the last patient last visit (LPLV).

5. Study population

Total number of patients: 374 considering 10% of expected dropouts.

Number of patients for each treatment arm = 168 (see Sample Size calculation for details).

6. Drug choice, tapering and maintenance daily dosages

The choice of the drug is left to the caring physician's discretion but it must be limited to the AEDs marketed for monotherapy use. All the study drugs will be used according to the respective SPCs, which will be sent by the promoter to all the study investigators.

For each individual drug, the following doses (in mg/day) have been selected as low vs. standard: carbamazepine, 300 vs 600; levetiracetam, 500 vs. 1000; valproate, 300 vs. 600; zonisamide, 150-300; oxcarbazepine, 600 vs. 1200; topiramate, 100 vs. 200; lamotrigine, 100 vs. 200; gabapentin, 450 vs. 900, lacosamide 100 vs. 200. Tapering to the assigned target dose will be performed as in

clinical practice but instructions will be imparted for each drug at the beginning of the study.

6.1 Treatment arms

- 1) *Low doses*
- 2) *Standard doses*

6.2 Concomitant Medications and Prohibited Treatments

Except for AEDs, there are no restrictions to the use of concomitant medications. For a correct outline of all drug interactions, the local investigator will be provided with the summary of product characteristics (SPC) of each individual AED used in the study. However, both subjects and investigators must keep records of all concomitant drugs on the concomitant medication page of the e-CRF along with daily dose and duration of use.

6.3 Patient numbering and treatment assignment

Eligible subjects will be enrolled and randomized during the same visit (Visit 1). At the end of this visit, if a subject fails to be randomized for any reason, the reason for not being randomized will be entered on the Screening Log.

Patients will be identified by a unique subject number, which will be assigned by the site investigator consecutively. The subject number will determine the allocation of treatment. The treatment will be assigned through a central randomization. The assigned treatment will be recorded in the source documents as well as in the subject's e-CRF. Once assigned, a subject number will not be reused for another patient. For all participants, the subject number will not be changed during the entire study.

6.4 Treatment blinding

The study is single-blind. Only the evaluating physician will be blinded to the assigned treatment schedule.

6.5 Brand & generic drugs

For each product, the treating physician can use the brand or the generic formulation. However, physicians and patients will be allowed to shift from brand to a generic formulation (where available) and vice versa and from one generic formulation to another during the study period.

6.6 Need to change the study drug or add another compound and premature withdrawal

An unscheduled phone contact will also take place soon after a relapse: the patients will also be instructed to call a member of the study staff within 24 h after an ictal event. If the study staff is confident about the epileptic nature of the event, the treating physician may decide to modify the treatment schedule; the patient will be thus instructed to change the AED doses or the treatment and come for the final visit within 72 hours. Otherwise, the patient will be invited to come for a clinic visit within the next 72 hours.

6.7 Study drugs dispensation

This is a not-for-profit study, according to Health Ministry Decree 17.12.2004. The same decree certifies that study drug costs are covered by the national health service (Art 2) in case of not-for-profit studies and if the study drug is used as per marketing authorization.

In this study, the drugs will be dispensed by the hospital pharmacies. When the patient receives the information on the drug and the daily dose assigned by randomization, he/she (or the treating physician) will contact the center's pharmacist to obtain the assigned drug. The drug will be reimbursed according to the directives imparted by each Italian region (eg, File F). Drugs will be labeled by pharmacists according to Vol 4 GMP, Annex 13, Labelling. All used (empty) and unused drug will be returned in the provided packaging to the investigator's staff for drug accountability. After being verified by the Clinical Monitor, all unused drug will be destroyed at the centre.

7. Visit schedule and assessments (see Study Flow Chart)

The recruitment period will last for 12 months and enrolled patients will be followed for 12 months after randomization. Enrolled patients will undergo periodic visits with a predetermined schedule:

7.1 Baseline evaluation.

The following assessments will be accomplished:

- a. Verification of all inclusion and exclusion criteria
- b. Recording of demographic data and clinical parameters: date of birth, sex, height, weight, arterial blood pressure and heart rate.
- c. Physical, neurological and psychiatric examination
- d. General clinical history: concomitant diseases and medications
- e. Assessment of birth control methods for women in childbearing age
- f. Family history of epilepsy, history of febrile seizures, date of onset, type of seizures, seizure

frequency at onset, epileptic syndrome or non-syndromic epilepsy

- g. Administration of the QOLIE-31 and PSQ-18 inventories
- h. Results of first interictal EEG
- i. Results of available blood sample withdrawal
- j. Imaging findings (MRI or CT scan as per clinical indication)
- k. Randomization and assignment of allocated treatment
- l. Delivery of seizure diary
- m. Appointment for the next visit at the discretion of the caring physician. First telephone contact at 4 weeks.

7.2 Follow-up visits.

Follow-up visits will be scheduled at the discretion of the caring physician but telephone contacts will be programmed at 4 weeks, 3, 6, 9 and an on-site clinic visit at 12 months. An interval of ± 1 week for the visit schedule is permitted. During each contact the patient will be asked to report any seizure recurrence, adverse event and any additional information deemed important for the management of the disease. Patients will be invited to read the diaries and verify if any missing or incomplete information was present.

The following evaluations will be performed during site visits:

1. Evaluation of possible relapses, compliance with treatment schedule and adverse events;
2. Recording of clinical parameters: weight, arterial blood pressure, heart rate;
3. Neurological examination;
4. General clinical history: concomitant diseases and medications;
5. Recording of the plasma concentration of the assigned drug and laboratory examinations previously specified (only if required as per clinical practice);
6. Administration of the QOLIE-31 and PSQ-18 inventories (only at 12 months);
7. Report of a standard, interictal EEG if performed as per clinical practice;
8. Report of the daily intake of assigned drug and timing of the assigned dose;
9. Report of all the contacts with the National Health System (NHS) for the management of seizures and AEDs;
10. Receipt of the seizure diary, control for quality and completeness, and delivery of a new diary.

The diaries will be examined by an investigator different from the treating physician (the evaluating physician) who will be blinded to the assigned drug schedule

The following evaluations will be performed during phone contacts:

1. Evaluation of possible relapses, compliance with treatment schedule and adverse events;
2. General clinical history: concomitant diseases and medications;
3. Report of the daily intake and timing of the assigned dose;
4. Report of a standard, interictal EEG, if performed;
5. Recording of the plasma concentration of the assigned drug and laboratory examinations previously specified, if performed;
6. Report of all the contacts with the NHS for the management of seizures and AEDs.

In case of seizure relapse or treatment change due to adverse events, the patient will exit the study and antiepileptic treatment will be modified if required by the treating physician.

